## Uploads

Upload the entire grant application(s)

D3 study.pdf

Upload copy(ies) of unbolded Consent Form(s)

D3 Control Subject CF 5 28 20 clean.pdf

D3 Depressed Subject CF 5 28 20 clean.pdf

Upload copy(ies) of bolded Consent Form(s)

D3 Control Subject CF 5 28 20 bold.pdf

D3 Depressed Subject CF 5 28 20 bold.pdf

Upload copy(ies) of recruitment materials/ads to be reviewed

Control Craigslist Ad (Revised).pdf

Control Qualtrics Facebook Survey (Revised).pdf

Depressed ad Craigslist (3rd revision).pdf

Depressed ad Qualtrics Facebook (3rd revision).pdf

Upload evidence of FDA Radiolabeled Drug approval(s)

151595 May Proceed.pdf

Upload copy(ies) of JRSC approval(s)

[name] NYSPI IRB 7976 APH-AABI3450 JRSC appr letter 4-23-2020.pdf

Upload a copy of Certificate of Confidentiality

Upload copy(ies) of the HIPAA form

D3\_HIPAA Authorization 4.4.20.pdf

Upload any additional documents that may be related to this study

MRI\_result\_letter\_1\_no\_findings.pdf

MRI\_result\_letter\_2\_followup.pdf

MRI\_result\_letter\_3\_irregular.pdf

MRI\_Director\_Approval\_D3 Study (signed).pdf

IND\_Decision\_Worksheet\_BR 4.13.20.pdf

Email\_IND decision for sinemet.pdf

Form of Notice by IND.IDE Holder 7.23.20.pdf

LDOPA Email Clarification.pdf

Statistical Analysis Plan

1/2 - Dopaminergic Dysfunction in Late-Life Depression (The D3 Study)

IRB #7976

NCT #04493320

Date: 10/03/19

C.11. DATA ANALYSES: We will examine variables for illegitimate values and outliers. The distribution of demographic variables and baseline characteristics will be examined across LLD (N=120) and never-depressed elder (NDE) subjects (N=60) as means, standard deviations, proportions, and 95% confidence intervals. As a precaution, indications of inequality between diagnostic groups (Aim 1) or the L-DOPA and placebo groups (Aim 2) in specific features (despite randomization) will trigger examination of whether differences in primary outcome measures may be attributed to group imbalances on background characteristics. For all analyses, significance tests will be reported after Benjamin-Hochberg adjustment controlling for FDR at level 0.05.

Analyses for Aim 1: By design the LLD and NDE subjects will be age and gender distribution matched. All analyses will control for site (2 sites). **Hyp 1:** The EEfRT analytic procedures will output data on the proportion of high-effort choices made, the relative influence of reward magnitude on making high-effort choices, and neural activations in the PFC and striatal ROIs. Depressed and never-depressed groups will be compared on these measures using linear regression models with group membership (LLD vs. NDE) as the primary predictor. In sensitivity analyses, NDE participants will be categorized as slowed (gait speed <1m/s) or non-slowed, and between-group comparisons will be performed to test LLD subjects vs. NDE-slow and NDE-non-slow groups. **Hyp 2:** Combining data from both LLD and NDE subjects, linear regression will assess associations between dopamine measures (specifically [¹⁸F]-FDOPA relative influx rate [K_{occ} in striatal ROI], [¹⁸F]-fallypride binding [BP_{ND} in midbrain and striatal ROIs], and mean NM-MRI signal intensity in the SNC) and primary RDoC outcome measures (behavioral/neural activation measures from the EEfRT, the processing speed latent factor, the NIH-EXAMINER Executive Composite score, and ST gait speed). Separate regressions will be fit for each of the RDoC outcome measures, including the different dopamine imaging measures as simultaneous predictors while controlling for demographics, site, and group status. Similar regression analyses will examine associations between the dopamine imaging measures and the first-level MIDT measures (i.e., neural activations on the anticipation and receipt of monetary reward contrasts in *a priori* ROIs), secondary cognitive outcomes, and secondary physical performance outcomes. **Hyp 3:** To further assess the degree to which slowing is a key pathway leading to the LLD phenotype, linear regression will test associations between the processing speed latent factor, NIH-EXAMINER Executive Composite score, ST gait speed, and the probability of choosing the HC/HR option on the EEfRT.

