## Specific Aims and Hypotheses

### Specific Aims and Hypotheses

The proposed study will enroll 60 elderly depressed outpatients who exhibit evidence of dopaminergic dysfunction, characterized as either slowed processing speed or slowed gait speed. To disentangle depression effects from age-related changes, 30 never-depressed elders also will complete baseline evaluation. Assessments include PET imaging of dopamine synthesis and receptor density, neuromelanin-sensitive MRI (NM-MRI) measurement of nigrostriatal status, task-based MRI focused on effort-based decision making and reward processing, and comprehensive psychiatric, neurocognitive, and physical performance evaluation. Depressed subjects then will be randomized to L-DOPA or placebo for 3 weeks, followed by repeat multimodal MRI and cognitive/behavioral assessments. In a cross-over phase,

---

participants will receive the opposite intervention for an additional 3 weeks followed by clinical and cognitive assessments only. This mechanistic probe allows us to examine the contributions and interrelationships of dopamine-dependent processes in LLD and evaluate the responsivity of dopamine systems to pharmacological stimulation.

**AIM 1:** To characterize dopaminergic dysfunction in LLD at molecular, circuit, and behavioral levels. **Hyp 1:** Compared to age- and gender-matched controls on baseline fMRI, LLD subjects will be less willing to expend effort for rewards and exhibit lower prefrontal cortex (PFC) and striatal activation on the Effort Expenditure for Rewards Task (EEfRT). **Hyp 2:** Across all subjects, lower striatal [18F]-FDOPA relative influx rate (Kocc), lower midbrain & striatal [18F]-fallypride binding, and lower NM-MRI signal in the substantia nigra, pars compacta (SNc) will predict lower performance across RDoC domains: Positive Valence (impaired willingness to expend effort, decreased neural activations on the EEfRT), Cognitive (slowed processing speed and executive dysfunction), and Sensorimotor (slowed gait speed). **Hyp 3:** Across all subjects, slowed processing and gait speed likewise will predict lower willingness to expend effort on the EEfRT.

**AIM 2:** To examine responsivity of dopamine circuits in LLD to stimulation with L-DOPA.

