#### Description of subject population

The N=60 Depressed sample will enroll subjects who are 1) aged 60 years old or greater, 2) have DSM5 diagnosis of Major Depressive Disorder (MDD) or Persistent Depressive Disorder, 3) Montgomery-Asberg Depression Rating Scale (MADRS) > 15, 4) decreased processing speed (1 SD below age-adjusted norms on the Digit Symbol Test) OR decreased gait speed (average walking speed on 15' course < 1m/s), and are 5) capable of providing informed consent and adhering to study procedures. Subjects will be excluded for 1) diagnosis of substance abuse or dependence (excluding Tobacco Use Disorder) in the past 12 months, 2) history of psychosis, psychotic disorder, mania, or bipolar disorder, 3) primary neurological disorder, including dementia, stroke, Parkinson's disease, epilepsy, etc., 4) MMSE < 24, 5) MADRS suicide item > 4 or other indication of acute suicidality, 6) current or recent (within the past 2 weeks) treatment with antidepressants, antipsychotics, or mood stabilizers, 7) history of hypersensitivity, allergy, or intolerance to L-DOPA, 8) any physical or intellectual disability adversely affecting ability to complete assessments, 9) acute, severe, or unstable medical illness, 10) mobility limiting osteoarthritis of any lower extremity joints, symptomatic lumbar spine disease, or history of joint replacement / spine surgery that limits mobility, 11) contraindication to MRI scanning, or 12) history of significant radioactivity exposure (nuclear medicine studies or occupational exposure).

The N=30 sample of Never-Depressed Elders will enroll subjects who are 1) aged  $\geq$  60 years), 2) have MADRS < 8, and are 3) capable of providing consent and adhering to study procedures. Exclusion criteria are identical to the Depressed Subjects, plus: (1) Any history of DSM 5 disorder and (2) family history of MDD in first-degree relative.

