## Inclusion/Exclusion Criteria

Name the subject group/sub sample

Depressed subjects

Create or insert table to describe the inclusion criteria and methods to ascertain them

Inclusion criteria

1. Age 60 years or older
2. DSM5 diagnosis of Major Depressive Disorder (MDD) or Persistent Depressive Disorder (PDD)
3. Montgomery Asberg Depression Rating Scale Score  $\geq 15$
4. Decreased processing speed or decreased gait speed
5. Capable of providing informed consent and adhering to study procedures

Methods of ascertainment

1. Clinical interview
2. SCID, clinical interview

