### Evaluation

1. Every subject (both potential Depressed participants and Never-Depressed participants) evaluated for this protocol will receive a clinical interview by a psychiatrist or psychologist. A psychiatrist or other qualified physician will see participants to evaluate medical aspects of eligibility, including screening for signs or symptoms of Parkinson's Disease (PD). If there is any concern, they will be referred to the study neurologist ([name] at Columbia). Additional assessments will be administered by a trained rater (BA, RN, or SW) in CAAM, including the Montgomery Asberg Depression Rating Scale (MADRS) and a SCID performed by a trained rater. Never-Depressed Elders will be selected for participation based on this initial assessment and clinical interview, while potential Depressed subjects will be further assessed as below.
2. If a subject has a diagnosis of Major Depressive Disorder (MDD) or Persistent Depressive Disorder (PDD), he/she will be informed of this and educated about the availability of treatments for depression. If a subject is not interested in depression treatment during the 6-8 weeks of study participation and/or prefers to begin with an experimental treatment for slowing and depression, he/she will be offered participation in the present study provided there is no suicidal ideation present. Based on the extant data supporting the efficacy

---

of antidepressants for MDD and PDD, they will be informed that antidepressant treatment would be a very reasonable option for their condition. These potential subjects will be offered the option of being referred out for depression treatment, and it will be clarified that L-DOPA is not as yet a treatment for MDD. Thus, all potential participants in this study must state their preference not to be treated with a standard treatment for depression.

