3. Next, trained raters (BA, RN, or SW) in CAAM will assess processing speed using the Digit Symbol test from the WAIS-III and the Trail-Making Test Part A. Digit Symbol or Trails A will be used as a selection criterion, with patients included in this study if they score 0.5 SD below the age-adjusted norms on Digit Symbol or Trails A. Patients' gait will be assessed by trained raters as walking speed in m/s on a Gaitrite walkway system. Patients are instructed to walk at their usual or normal speed starting and ending at a point 6 feet prior to and after the walkway course to eliminate acceleration and deceleration effects. Two trials will be completed, and gait speed will be based on the average of 2 trials. Gait speed will be used as a selection criterion, with patients included in this study if they have a gait speed < 1 m/s.

4. If subjects are eligible for the study after review of their processing speed and gait speed and decide to participate by signing informed consent, then they will complete the remainder of the baseline assessment. This includes recording of each subject's chief complaint, referral source, age of onset of mood and/or cognitive decline, number prior depressive episodes, age, sex, marital status, race and ethnicity, years of education, employment status and income, years of education, family history. We also will document medical history, physical exam, urine drug screen, CBC, chemistries and electrolytes, thyroid profile, vitamin B12 and folate levels, urine analysis, and ECG. Vital signs will be measured at baseline and monitored weekly throughout the study. The Cumulative Illness Rating Scale-Geriatric (CIRS-G) will be filled out at baseline to measure chronic medical illness burden. Subjects' current physical pain will be assessed weekly using a 100mm Pain Visual Analog Scale (VAS) and used as a covariate in analyses of gait speed.

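### The Aim 1 sensitivity analysis calls controls slowed on gait alone, although depressed subjects qualify on gait or processing speed

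*SAP*

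**What the plan says.** **Depressed group.** The protocol's Specific Aims describe the dopaminergic dysfunction required for entry as "characterized as either slowed processing speed or slowed gait speed". The Description of subject population asks for "decreased processing speed (1 SD below age-adjusted norms on the Digit Symbol Test) OR decreased gait speed", and the Inclusion/Exclusion table lists "Decreased processing speed or decreased gait speed". Study Procedures, Evaluation, item 3 keeps the either/or structure but sets a different cognitive threshold: patients enter "if they score 0.5 SD below the age-adjusted norms on Digit Symbol or Trails A".

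**Controls.** No slowing criterion appears in either list of control criteria. Evaluation, item 1 states that "Never-Depressed Elders will be selected for participation based on this initial assessment and clinical interview".

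**Analysis.** SAP section C.11, Aim 1 Hyp 1, compares the groups on the effort task (EEfRT) by linear regression with diagnostic group as the main predictor. Site is adjusted for in all Aim 1 analyses, and no slowing covariate is named. A sensitivity analysis follows, in which "NDE participants will be categorized as slowed (gait speed <1m/s) or non-slowed". Each of these two control subgroups is then set against the depressed group, which is not itself split by type of slowing.

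**The concern.** Every depressed subject is selected for slowing and no control is, so the main contrast carries slowing along with depression. The sensitivity analysis is where the plan takes this up, but it uses only one of the two entry routes and gives no reason for leaving out the other.

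Processing speed is not incidental to the outcome. Aim 1 Hyp 3 predicts that slowed processing, as well as slowed gait, goes with less willingness to expend effort, and background section A.7 argues that slowing raises the cost of effort. On the investigators' own account, then, the omitted route can affect the quantity being compared. If depressed subjects differ from gait-slowed controls in processing speed, a remaining difference in effort could be read as depression when part of it is cognitive slowing. The non-slow reference group is also blurred, because it can contain people whom the study elsewhere regards as slowed.

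**Working it through.** **Step 1: apply both rules to the same profile.** Take any one processing-speed cut-off.

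| Processing speed | Gait | If depressed | If control (SAP) |
|---|---|---|---|
| slowed | below 1 m/s | meets slowing criterion | slow |
| slowed | 1 m/s or above | meets slowing criterion | **non-slow** |
| not slowed | below 1 m/s | meets slowing criterion | slow |
| not slowed | above 1 m/s | does not meet it | non-slow |

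Only the second row disagrees. Cognitively slowed controls who also walk slowly are classed as slow under either rule.

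**Step 2: see whether another specified analysis fills the gap.** Hyp 2 adjusts for group, but its predictors are the dopamine imaging measures and the speeds are outcomes. Hyp 3 relates both speeds to effort choice but does not name group as a covariate. The opening of C.11 promises to examine whether differences in primary outcomes could come from imbalance in background characteristics; that check is conditional and names neither slowing nor a model.

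**Step 3: gauge the size.** The plan gives no figure to reproduce, so this rests on assumptions.

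- Number of controls: 60 over two sites (SAP); 30 at this site (protocol).
- Cognitive cut c: 1 SD or 0.5 SD below the age norm (both in the protocol).
- Assumed: control scores follow the norms, so P(slowed) = Φ(−1) = 0.1587 or Φ(−0.5) = 0.3085. That is 60 × 0.1587 = 9.5 or 60 × 0.3085 = 18.5 controls before gait is considered.
- Assumed: the share of controls below 1 m/s, g, is 10% to 40%.
- Assumed: processing speed and gait are bivariate normal with correlation ρ from 0 to 0.5.

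The misfiled share of all controls is m = P(slowed) − P(slowed and gait below 1 m/s). The count is 60m, and the share of the non-slow group is m/(1 − g). For example, with ρ = 0, g = 0.10 and the 1 SD cut, m = 0.1587 × 0.90 = 0.143, so 60m = 8.6 and m/(1 − g) = 0.143/0.90 = 15.9%.

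| Cut | ρ | g | m | Of 60 | Share of non-slow group |
|---|---|---|---|---|---|
| 1 SD | 0 | 0.10 | 0.143 | 8.6 | 15.9% |
| 1 SD | 0.3 | 0.20 | 0.104 | 6.2 | 13.0% |
| 1 SD | 0.5 | 0.40 | 0.045 | 2.7 | 7.5% |
| 0.5 SD | 0 | 0.10 | 0.278 | 16.7 | 30.9% |
| 0.5 SD | 0.3 | 0.20 | 0.215 | 12.9 | 26.9% |
| 0.5 SD | 0.5 | 0.40 | 0.112 | 6.7 | 18.7% |

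For the 30 controls at this site the counts are 1.4 to 4.3 and 3.4 to 8.3. Of all controls slowed by the depressed group's rule, the fraction labelled non-slow is m/(g + m): from 0.045/0.445 = 10% to 0.143/0.243 = 59% at 1 SD, and from 0.112/0.512 = 22% to 0.278/0.378 = 74% at 0.5 SD. The 0.5 SD rows count one test only; allowing Trails A as a second way to qualify would raise them.

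**The case against.** A reader might infer more than the documents support, in four respects.

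- *That nothing else in the plan bears on depression versus slowing.* Hyp 3 tests both speeds against effort choice across all subjects, and the imbalance check could be extended to slowing. Neither is a specified group contrast that accounts for slowing, so the narrower statement stands.
- *That controls were enrolled to separate depression from slowing.* The Specific Aims say they are there to separate depression from changes that come with age, and the SAP matches the groups on age and gender distribution. Slowing also lies on the hypothesised path to reduced effort, so a difference carried by slowing is partly the theory under test and not simply confounding.
- *That the Hyp 1 result is undermined.* The main comparison is the same however controls are subdivided.
- *That the counts follow by multiplying the two prevalences.* That assumes independence. Background section A.5 says gait control shares frontal-subcortical circuits with executive function and attention, so a positive correlation is plausible and lowers the counts. The exclusions for controls (any DSM-5 disorder, neurological disease, MMSE below 24, unstable illness) may also make slowing rarer than the norms imply.

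Two practical objections also have force. The cognitive cut-off is not one rule: the Description of subject population and the Inclusion/Exclusion table use 1 SD on Digit Symbol, whereas under Evaluation, item 3 "Digit Symbol or Trails A will be used as a selection criterion", at 0.5 SD. And the documents do not show that controls receive Trails A: item 1 reserves the further screening for potential depressed subjects, and the measures listed for the processing-speed outcome do not include it. The companion site works under its own protocol, which is not available here. Finally, even an either/or stratum may differ from the depressed group in the mix and severity of slowing.

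**Conclusion.** The mismatch is plain from the text and depends on none of the assumed figures. Followed as written, the SAP labels cognitively slowed controls with gait of at least 1 m/s as non-slow, and compares depressed subjects slowed by either route with controls slowed by gait. A remaining difference from the slow controls could then reflect cognitive slowing.

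Under the stated assumptions, about 3–9 of 60 controls are misfiled at the 1 SD cut (8–16% of the non-slow group), or 7–17 at the 0.5 SD cut (19–31%), and fewer if controls are healthier than the norms. The flaw is confined to a sensitivity analysis. It should be corrected because the plan breaks its own definition of slowing in the one specified Hyp 1 contrast that takes slowing into account.

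**What to change.** 1. **Reconcile the entry rule first.** The protocol must settle on one processing-speed criterion (1 SD on Digit Symbol, or 0.5 SD on Digit Symbol or Trails A). It must also settle the gait boundary, which is below 1 m/s in most places but at or below 1 m/s in the Inclusion/Exclusion table. The SAP should name the test version and norms too, since the protocol refers both to Digit Symbol (WAIS-III) and to Coding (WAIS-IV).
2. **Change the sentence in SAP C.11, Aim 1 Hyp 1.** Class controls as slowed by the same either/or rule, from baseline gait and the Digit Symbol/Coding score. Keep the gait-only split as a secondary display.
3. **Add one sensitivity model.** Put continuous processing speed and gait speed into the regression of effort outcomes on group, to allow for differences in mix and severity that strata leave behind. State beside it that slowing may lie on the hypothesised pathway, so a smaller adjusted difference does not by itself show confounding.

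The cost is modest. Hyp 2 already uses processing speed and gait in both groups, and the protocol Overview includes controls in baseline neurocognitive and physical performance testing. New data would be needed only if the reconciled rule keeps Trails A and controls do not receive it. The non-slow group shrinks: in the cases above, from 54 to about 45 (54 − 8.6) or from 36 to about 33 (36 − 2.7) at 1 SD, and from 54 to about 37 (54 − 16.7) or from 36 to about 29 (36 − 6.7) at 0.5 SD. There are one or two more sensitivity models to report.
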